GGT	Gamma Glutamyl Transferase
Hb	Hemoglobin
HDL	High-density Lipoprotein
HPLC/MS-MS	High-Performance Liquid Chromatography/Tandem Mass Spectrometry
Hct	Hematocrit
IB	Investigator's Brochure
ICF	Informed Consent Form
ICH	International Conference on Harmonization
IEC	Independent Ethics Committee
IHC	Immunohistochemistry
IND	Investigational New Drug
INR	International Normalized Ratio

Abbreviation	Definition
IP	Investigational Product
IRB	Institutional Review Board
ITT	Intent-to-Treat
K_{el}	Elimination Constant
LDL	Low-density Lipoprotein
MedDRA	Medical Dictionary for Regulatory Activities
MCH	Mean Corpuscular Hemoglobin
MCHC	Mean Corpuscular Hemoglobin Concentration
MCV	Mean Corpuscular Volume
MRI	Magnetic Resonance Imaging
MRT	Mean Residence Time
MTD	Maximum Tolerated Dose
NCV	Nerve Conduction Velocity
ORR	Objective Response Rate
OS	Overall Survival
PD	Progressive Disease
PFS	Progression-Free Survival
PK	Pharmacokinetic
PP	Per-Protocol
PR	Partial Response
PT	Prothrombin
RBC	Red Blood Cell
RECIST	Response Evaluation Criteria in Solid Tumors
Rx	Administration of SCB01A
SAE(s)	Serious Adverse Event(s)
SD	Stable Disease
SOP	Standard Operating Procedure
$t_{1/2}$	Half-life
TEAE	Treatment Emergent Adverse Event
TG	Triglycerides
T_{max}	Time to Maximum Concentration
ULN	Upper Limit of Normal
V_d	Volume of Distribution
WBC	White Blood Cell

Table 1: Study Schedule, Screening, and Treatment Phase

Study Visit[1]	Screening	Cycle 1			Cycle 2			Cycle 3			EOT[1] [2]	Early Withd rawal	Unsched uled	
		C1D1		C1D8	C1D15	C2D1	C2D8	C2D15	C3D1	C3D8				C3D15
		PreRx	PostRx											
Study Days	-28 to -1	1 (±0)		8 (±1)	15 (±2)	22 (±1)	29 (±1)	36 (±2)	43 (±1)	50 (±1)	57 (±2)	64 (±2)	NA	NA
Study Weeks		0		1	2	3	4	5	6	7	8	9	NA	NA
Activities														
Informed Consent	X													
Medical History	X	X												
Demographics	X													
Eligibility Criteria	X													
Physical Examination	X	X		X	X	X	X	X	X	X	X	X	X	X
Vital Signs	X	X	X	X	X	X	X	X	X	X	X	X	X	X
BSA Calculation		X		X		X	X		X	X				
ECOG Performance Status	X	X		X	X	X	X	X	X	X	X	X	X	X
Adverse Events Review[3]			X	X	X	X	X	X	X	X	X	X	X	X
Concomitant Medication Review	X	X	X	X	X	X	X	X	X	X	X	X	X	X
12-Lead ECG	X	X[4]	X[4]	X[4]		X[4]	X[4]		X[4]	X[4]		X	X	X [13]
Radiological Image Assessments[5]	X											X	X	X [13]
Laboratory Assessments[6]	X	X[8]		X	X	X	X	X	X	X	X	X	X	X [13]
Urinalysis[7]	X	X[8]				X			X			X	X	X [13]
PK Blood Sample Collection [9]									X	X				
Serum Pregnancy Test [10]	X													
Study Drug Administration [11]		X		X		X	X		X	X				
Nerve Conduction Velocity [12]	X													

[1] Subjects may continue treatment beyond 3 cycles (9 weeks) of SCB01A treatment per investigator discretion if they are experiencing clinical benefit, until the study is terminated. Refer to Table 2 for the schedule of assessments for additional treatment cycles.

[2] EOT visit should be conducted 14 or 21 days (±2 days) after last infusion, depending on last infusion was given on Day 8 or Day 1, respectively. Early withdrawal visit should be conducted after the subject received the last dose of study treatment. A toxicity follow-up (can be done by phone contact) should be performed 28±3 days after the last dose of study treatment.

- [3] All AEs including SAEs must be reported from the time of start of study treatment and must continue to be followed for 28 days after last administration of study treatment.
- [4] ECG will be performed prior to study drug administration (pre-infusion), and then at 10 and 24 hours after the start of infusion on Days 1 and 8 of Cycles 1, 2 and 3 and at pre-infusion and 24 hours after the start of infusion on Days 1 and 8 of Cycles beyond Cycle 3 (time window at each sample collected: ± 30 min).
- [5] Tumor assessments should be performed at baseline and at the end of Cycle 3 (at C4D1/EOT visit). Any additional assessment can be arranged when clinically indicated.
- [6] Hematology: Hemoglobin, Hematocrit, MCV, MCHC, MCH, RBC count, WBC count, WBC Differential, Absolute neutrophil count and Platelet count
Coagulation: PT, and INR
Chemistry: Total Bilirubin, Alkaline Phosphatase, ALT, AST, Gamma-glutamyl transferase (GGT), Albumin, Total Protein, Creatinine, Urea (BUN), Uric acid, Total Creatinine Kinase (Ck) (if total Ck is above the ULN for the laboratory, Troponin-T or Troponin-I will be determined), Sodium, Potassium, Calcium, Chloride, Glucose, Triglycerides (TG) and Amylase.
The following lab panel will only be assessed at Screening Visit and EOT/Early Termination Visit: Creatinine Clearance, Total Cholesterol, High-Density Lipoprotein (HDL), Low-Density Lipoprotein (LDL) and Lipase.
The following lab panel will only be assessed at Screening Visit: Hepatitis B/C
- [7] Urinalysis: pH, Appearance, Color, Specific gravity, Viscosity, Turbidity, Ketones, Bilirubin, Blood, Glucose, Protein, Nitrites, Urobilinogen, Leukocyte esterases, Microscopic exam includes bacteria, cast, crystals, epithelial cells, RBC, and WBC.
- [8] Hematology, clinical chemistry and urinalysis test results within 2 days prior to Cycle 1, Day 1 (C1D1) are acceptable. Only items not performed or obtained within 2 days prior to C1D1 should be tested.
- [9] PK will only be performed on subjects enrolled in Stage I. PK blood samples will be taken immediately pre-infusion then at 24, 25, 26, 28 and 32 hours after the start of infusion on Days 1 and 8 of Cycle 3 if dose level of Cycle 3 is $24\text{mg}/\text{m}^2$ (time window at each sample collected: ± 5 min).
- [10] Serum pregnancy test for women of childbearing potential must be performed ≤ 14 day prior to first dose.
- [11] i.v. infusion for 24-hour of SCB01A on Days 1 and 8 of each cycle in a 3-week cycle (time window: 24 hours ± 10 min).
- [12] To be performed for all subjects at baseline and then during the trial only if grade 2 or above neurological symptoms experienced by the subject after receiving treatment with SCB01A. Refer [Section 5.9](#) for further details.
- [13] To be performed when necessary at the subject's request or per Investigator decision.

Table 2: Study Schedule, Additional Treatment Cycles/Visits

Study Visit ^[1]	Cycle 4			Cycle 5			Additional Cycles			EOT ^[2]	Early Withdrawal	Unscheduled
	C4D1	C4D8	C4D15*	C5D1	C5D8	C5D15*	CxD1	CxD8	CxD15*			
Study Days	64 (±1)	71 (±1)	78 (±2)	85 (±1)	92 (±1)	99 (±2)	NA	NA	NA	NA	NA	NA
Study Weeks	9	10	11	12	13	14	NA	NA	NA	NA	NA	NA
Activities												
Physical Examination	X	X		X	X		X	X		X	X	X
Vital Signs	X	X		X	X		X	X		X	X	X
BSA Calculation	X	X		X	X		X	X				
ECOG Performance Status	X	X		X	X		X	X		X	X	X
Adverse Events Review ^[3]	X	X		X	X		X	X		X	X	X
Concomitant Medication Review	X	X		X	X		X	X		X	X	X
12-Lead ECG	X ^[4]	X ^[4]		X ^[4]	X ^[4]		X ^[4]	X ^[4]		X	X	X ^[10]
Radiological Image Assessments ^[5]	X									X	X	X ^[10]
Laboratory Assessments ^[6]	X	X		X	X		X	X		X	X	X ^[10]
Urinalysis ^[7]	X			X			X			X	X	X ^[10]
Study Drug Administration ^[8]	X	X		X	X		X	X				
Nerve Conduction Velocity ^[9]												

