***No Day 15 visit starting from Cycle 4**

- [1] Subjects may continue treatment beyond 3 cycles (9 weeks) of SCB01A treatment per investigator discretion if they are experiencing clinical benefit, until the study is terminated. Refer to Table 2 for the schedule of assessments for additional treatment cycles.
- [2] EOT visit should be conducted 14 or 21 days (±2 days) after last infusion, depending on last infusion was given on Day 8 or Day 1, respectively. Early withdrawal visit should be conducted after the subject received the last dose of study treatment. A toxicity follow-up (can be done by phone contact) should be performed 28±3 days after the last dose of study treatment.
- [3] All AEs including SAEs must be reported from the time of start of study treatment and must continue to be followed for 28 days after last administration of study treatment.
- [4] ECG will be performed prior to study drug administration (pre-infusion, 0 hr), and then at the end of the infusion (24 hr) on Days 1 and 8 of additional treatment cycles beyond Cycle 3 (time window at each sample collected: ±30 min).

- [5] Tumor assessments will be assessed by using computerized tomography (CT) or MRI scans according to RECIST v1.1 at baseline, end of the first 3 cycles, and every three cycles thereafter until progression of disease (i.e. at or within 4 days prior to Day 1 of Cycle 4, 7, 10 and so on). For subjects who meet objective response criteria after the first 3 cycles of study treatment, confirmative radiological tumor assessments will be performed at least 4 weeks later.
- [6] Hematology: Hemoglobin, Hematocrit, MCV, MCHC, MCH, RBC count, WBC count, WBC Differential, Absolute neutrophil count and Platelet count
Coagulation: PT, and INR
Chemistry: Total Bilirubin, Alkaline Phosphatase, ALT, AST, Gamma-glutamyl transferase (GGT), Albumin, Total Protein, Creatinine, Urea (BUN), Uric acid, Total Creatinine Kinase (Ck) (if total Ck is above the ULN for the laboratory, Troponin-T or Troponin-I will be determined), Sodium, Potassium, Calcium, Chloride, Glucose, Triglycerides (TG) and Amylase.
The following lab panel will only be assessed at Screening Visit and EOT/Early Termination Visit: Creatinine Clearance, Total Cholesterol, High-Density Lipoprotein (HDL), Low-Density Lipoprotein (LDL), and Lipase.

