3.2.2. Cycle 1, Day 1 (C1D1)

The following procedures/assessments will be performed:

Pre-treatment

- Record pre-existing conditions (baseline signs and symptoms with an onset between time of signing the informed consent and the first dose of study drug)
- Physical examination
- Vital signs
- Calculation of body surface area (BSA)
- ECOG performance status
- Concomitant medication
- 12-lead ECG
- Laboratory tests (hematology*, clinical chemistry* and coagulation)
- Urinalysis*

*Test results within 2 days are acceptable, only items not performed for screening within 2 days before this visit need to be tested again.

Study Drug Administration

- Study treatment - i.v. infusion for 24-hour of SCB01A

Post-initiation of Study Drug Administration

- Vital signs
- AEs
- Concomitant medication
- 12-lead ECG - *At 10 and 24 hours after the start of infusion*

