4.4. Study Drug Dose Preparation and Administration

The study drug, SCB01A is packaged as 10 mg/ml in 5 ml/vial. The injection volume of SCB01A should be calculated based on the BSA of the subject. (See [Section 5.3](#)). The study drug will be diluted in normal saline solution before infusion. An equal volume of normal saline will be drawn out from a 250 ml normal saline container before adding the SCB01A injection solution. The total volume of study drug diluted solution will be equal to 250 ml. The study drug should be administered for 24 hours (time window 24 hours±10 mins) by i.v. infusion through a central line in order to avoid potential extravasation and tissue necrosis. The duration from drug dilution to completion of 24h i.v. infusion must not exceed a maximum of 28 hours. For further details, please refer to the IMP Manual.

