7.2. Adverse Event Reporting

All AEs occurring during the study (from the time of the first study treatment until 28 days after the last dose of study treatment) observed by the Investigator or reported by the subject (whether or not attributed to study drug), will be reported on the CRF. Clinically significant AEs considered related or non-related to the IP by the Investigator or the Sponsor will be followed until resolved or considered stable by the Investigator. The following information must be provided: description; dates of onset and resolution; severity; assessment of relatedness to IP, other suspect drug, or device; and action taken. The investigator may be asked to provide follow-up information.

All AEs, serious or not, that result in the subject's permanent withdrawal of IP or from the study will be discussed between the investigator and medical monitor. The CRF for EOT/Early Withdrawal Visit should be completed including reason of withdrawal.

It will be the investigator's clinical judgment whether or not an AE is of sufficient severity to require the subject's removal from study treatment. A subject may also voluntarily withdraw from study treatment due to what he or she perceives as an intolerable AE. If either of these occurs, the subject must undergo EOT assessment and be given appropriate care under medical supervision until symptoms cease or the condition becomes stable.

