7.3. Serious Adverse Events (SAEs)

An SAE is defined as any untoward medical occurrence that at any dose (ICH E2A and E6 R1):

- Results in death.
- Is life-threatening.
This means that the subject is at risk of death at the time of the event; it does not mean that the event hypothetically might have caused death if it were more severe.
- Requires inpatient hospitalization or prolongation of existing hospitalization.
- Results in persistent or significant disability or incapacity.
- Is a congenital anomaly or birth defect.

Other important medical events that may not be immediately life-threatening or result in death or hospitalization, based upon appropriate medical judgment, are considered SAEs if they are thought to jeopardize the subject and/or require medical or surgical intervention to prevent one of the outcomes defining a SAE.

Since SAEs are critically important for the identification of significant safety problems, it is important to take into account both the Investigator's and the sponsor's assessment. If either the sponsor or investigator believes that the event is serious, the event must be considered serious and evaluated by the Sponsor for expedited reporting.

All SAEs must be reported to the sponsor or sponsor designee immediately after the Investigator becomes aware of the event, along with a determination as to whether it is associated with the IP or any other study procedure.

Disease progression should not be recorded as an AE or SAE term; instead, signs and symptoms of clinical sequelae resulting from disease progression will be reported if they fulfill the SAE definition.

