7.4. Serious Adverse Event Reporting

All SAEs, irrespective of relationship to IP, must be reported within 24 hours of the Investigator knowledge of the event to the Sponsor or CRO. In particular, if the SAE is fatal or life-threatening, notification to the Sponsor must be made immediately, irrespective of the extent of available AE information. This timeframe also applies to follow-up information on previously forwarded SAE reports as well as to the initial and follow-up reporting of exposure during pregnancy and exposure via breast feeding cases.

Relevant medical records should be provided to the Sponsor or CRO as soon as they become available; autopsy reports should be provided for deaths if available. Should an Investigator be made aware of an SAE occurring any time after the reporting period, it must be promptly reported.

All SAEs that have not resolved by the end of the study, or that have not resolved upon discontinuation of the subject's participation in the study, must be followed until any of the following occurs:

- The event resolves.
- The event stabilizes.
- The event returns to baseline, if a baseline value/status is available.
- The event can be attributed to agents other than the IP or to factors unrelated to study conduct.
- It becomes unlikely that any additional information can be obtained (subject or health care practitioner refusal to provide additional information, lost to follow-up after demonstration of due diligence with follow-up efforts).

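### SAE reporting opens at the first infusion, so a serious complication of a central line placed for the study before then has no clearly required SAE report

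*Protocol*

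**What the plan says.** The reporting window is stated three times in the protocol, each time with the same start. Footnote 3 to Table 1 reads "All AEs including SAEs must be reported from the time of start of study treatment and must continue to be followed for 28 days" after the last administration, and footnote 3 to Table 2 repeats it. Section 7.2 puts the period as "from the time of the first study treatment until 28 days after the last dose of study treatment". In Table 1 the adverse event review is first marked at C1D1 after treatment; Screening and C1D1 before treatment have no mark on that row.

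Section 4.4 has the drug given "by i.v. infusion through a central line in order to avoid potential extravasation and tissue necrosis", with no exception. Section 3.2.2 has sites record pre-existing conditions before the first dose, which it describes as "baseline signs and symptoms with an onset between time of signing the informed consent and the first dose of study drug". Section 7.3 requires SAEs to go to the sponsor "along with a determination as to whether it is associated with the IP or any other study procedure". Section 7.4 sets the 24-hour rule and has one provision for events outside the window: "Should an Investigator be made aware of an SAE occurring any time after the reporting period, it must be promptly reported".

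The SAP text supplied does not address when AE or SAE collection begins.

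**The concern.** A central line is part of how this regimen is delivered, so harm from placing one for the study belongs in its safety record. Section 7.3 recognises that an SAE can come from a study procedure. Yet if the line is placed for the study, placement necessarily comes before the first infusion, and so before SAE reporting opens.

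A serious bleed or pneumothorax at placement could then be written down as a baseline condition. It would have no clearly required SAE form, no 24-hour notice to the sponsor and no causality assessment. If the complication prevented dosing altogether, the subject would also be missing from the safety analysis. What is at stake is the completeness of the safety record. The ORR analysis, the sample size and the stopping rule are unaffected.

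**Working it through.** The plan gives no figure on this point and no arithmetic applies. The check is a comparison of the sections.

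1. **When reporting opens.** Footnote 3 of Tables 1 and 2 and section 7.2 agree on the first study treatment. The footnotes name SAEs expressly, so the start is not limited to non-serious events.
2. **When the line must exist.** Under section 4.4 it must be in place when the first infusion starts. Placement is not scheduled anywhere: it is missing from the visit lists in 3.2.1 and 3.2.2 and from Table 1.
3. **The interval at issue.** Screening runs from Day -28 to Day -1, so up to 28 days can separate consent from the first infusion.
4. **What happens to an event in that interval.** Section 3.2.2 records it as a pre-existing condition. Medical history is marked at C1D1 before treatment in Table 1; adverse event review is not.
5. **Whether another rule reaches back.** The out-of-window provision in 7.4 looks only forward, to SAEs after the period. Sections 7.1.1, 7.3 and 7.4 also contain broad sentences with no start date, considered under the objection.
6. **Who is analysed.** Safety is analysed on the ITT population (protocol synopsis; SAP 9.7.1.2), which requires at least one study treatment (protocol 8.3; SAP 9.7.1.1). A consented subject who is never dosed is outside it.

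Putting these together for a line-placement complication:

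| Situation | Position under the stated window |
|---|---|
| Line already in place before consent | Placement is not a study procedure; outside this point |
| Placed for the study; onset after consent and before first dose; no later worsening | Outside the window; at most a pre-existing condition |
| Same onset, but worsens on or after first dose | A TEAE under section 8.4; captured |
| Onset from first dose to 28 days after last dose | Inside the window of section 7.2; captured |
| Placed for the study; subject never dosed | Outside the window and outside the ITT population |

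The gap is the second and fifth rows. In both, section 7.3 asks for a judgement on procedure-relatedness, but the stated window does not open early enough to require it.

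**The case against.** The strongest reply is that section 4.4 specifies a route and does not make insertion a study procedure. All eligible subjects have had platinum treatment, and some may already have a line. Section 4.4 also refers to an IMP Manual that is not among the documents. This stands: the point applies only where a line is placed for the study after consent.

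A second reply is that the broad sentences already cover the case. Section 7.1.1 sends AEs from any cause arising during the study to the Safety Coordinator, 7.3 sends every SAE to the sponsor, and 7.4 applies the 24-hour rule whatever the relationship to the drug. A careful site might report on that basis. Nor does section 3.2.2 say that a serious event is exempt from SAE handling. But none of these sentences gives a start date, while the footnotes and 7.2 do. The texts conflict, and the more specific one leaves the event out. It would therefore be too strong to say that such an event certainly goes unreported; the supportable statement is that reporting is not clearly required.

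Third, much line-related risk is captured. Infection or thrombosis with onset during treatment is inside the window, and section 8.4 counts earlier events that worsen after first dose, as well as events with a missing onset date. A reader might infer that the safety tables show no line risk at all, or that every event before the first dose is lost. Neither follows: later events are tabulated, and earlier ones may still be on file under section 3.2.2.

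Fourth, starting AE collection at first dose is stated consistently and matches the TEAE definition. That is a sound reason to leave general AE collection alone. It does not answer the narrower question about SAEs from required procedures.

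**Conclusion.** The concern holds in a limited form. For a subject whose central line is placed for the study after consent, a serious placement complication that begins before the first infusion and does not worsen after it falls outside the stated SAE window. Nothing elsewhere in the protocol clearly brings it back in.

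The size cannot be worked out. The documents give neither the number of subjects needing a new line, which could be anywhere from none to all of the planned maximum of 37, nor a complication rate. The number of events is likely to be small. An expected count would have to rest on invented inputs, so none is given.

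A reader might also infer that the window keeps the DSMB uninformed. The documents do not support that. The listed occasions for DSMB review in section 3.1 are unresolved Grade 2 neurotoxicity, Grade 3 or higher neurotoxicity, and completion of 10 evaluable Stage I subjects. A line-related SAE inside the window is not among them either.

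This is a low-cost improvement to safety reporting, not a defect that threatens the trial's conclusions.

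**What to change.** In section 7.2 and in footnote 3 of Tables 1 and 2, make SAEs related to protocol-required procedures, including central-line placement for the study, reportable from signed consent under the 24-hour rule of section 7.4. Reconcile sections 3.2.2, 7.1.1, 7.3 and 7.4 with that start, so that recording a condition as pre-existing does not replace an SAE report.

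List these SAEs separately from TEAEs, and include those in consented subjects who are never dosed. Leave general AE collection and the TEAE definition at first dose.

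The cost is protocol wording and a few additional SAE forms. The supplied SAP text is written in the past tense. If the study has already been conducted, the report should say that procedure-related SAEs before dosing were not systematically collected, and the records made under section 3.2.2 should be checked for line complications.
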